6.2. Endpoints

All endpoints (i.e., outcomes) are summarized as above mentioned under section 5.1 and by visit.

6.3. Subjects

Inclusion criteria

For inclusion in the clinical investigation, the subject must fulfill all of the below criteria prior to enrollment and after enrollment (i.e., screening phase and enrollment phase).

For inclusion in the investigation of patient-subjects:

1. Age > 18 years.
2. Ophthalmological disease, disorder, illness or problem.
3. Provision of informed consent i.e., subject must be able to understand and sign the patient information and consent form.

For inclusion in the investigation, the healthy subjects:

1. Age > 18 years.
2. Without known eye disease.
3. Provision of informed consent i.e., subject must be able to understand and sign the patient information and consent form.

Exclusion criteria

Subjects who meet any of the below criteria, during screening phase and/or enrollment phase) will be excluded from the investigation.

For the exclusion of patients-subjects:

1. Patients with narrow-angle glaucoma.
2. Inclusion in other ongoing investigations at present that would preclude the subject from participating in this investigation as judged by the Principal Investigator.

For the exclusion of healthy subjects:

1. Presence of eye disease, eye trauma, diabetes or pregnancy.
2. Inclusion in other ongoing investigations at present that would preclude the subject from participating in this investigation as judged by the Principal Investigator.

Subject eligibility

Once written informed consent has been obtained, the Case Report Form and Subject prescreening and screening log will be completed to document adherence to the inclusion and exclusion criteria.

Where a subject fails to fulfil any element of the inclusion and exclusion criteria, this will be documented and the signed consent form and completed inclusion/exclusion criteria retained by the Principal Investigator. The subject will not be advanced any further into this clinical investigation.

Subject identification

When a subject is identified and considered eligible for entry to this clinical investigation, the subject will be allocated the next available investigation number (i.e. enrolment number) and the enrolment of the patient must be recorded in the Subject Enrolment Identification log.

For subjects enrolled, this number will consist of 01 for the first subject, 02 for the second subject and so on. This number will be the unique identifier of the subject (i.e. enrolment number) and written on each page of the paper/electronic Case Report Form booklet and all other documentation relating to that subject.

Each subject that is enrolled into the study will have their study participation recorded in their medical records, a copy of their signed and dated consent form and a patient information sheet should also be placed on his patient files to identify the subject as participating in a clinical investigation.

Investigation population

The investigation population are healthy persons and patients (120 subjects in total).

Approximately 100 male or female subjects, 18 years or older, with an ophthalmological disease, disorder, illness or problem will be recruited in this investigation.

Approximately 20 healthy male or female subjects, 18 years or older, will be recruited in this investigation.

The investigation population is not a *vulnerable population* as described by GCP.

Criteria and procedures for subject withdrawal or discontinuation

Subjects are free to discontinue participation in the clinical investigation at any time, and without prejudice to further treatment. Subjects who discontinue the clinical investigation should always be asked about the reason(s) for their discontinuation and about the presence of any AE/ADE or DD and, if possible, be assessed by an investigator. AE/ADE should be followed up. Subjects will be informed clearly they have no obligation to give a reason for discontinuation or to answer other questions.

Subjects may be withdrawn from clinical investigation at any time, at the discretion of the investigator.

Incorrectly enrolled subjects will be withdrawn from further clinical investigation. A subject may, however, continue the investigation under special circumstances (i.e., if continuation of investigation or follow-up actions are necessary for the subject's safety and well-being, and the continuation of the investigation is not expected to be associated with any risk or discomfort for the subject).

When a subject redraws or is discontinued from the research, the subject recruitment continues until the defined number of both patient and healthy subjects are maintained in the study dataset.

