	
such as hemorrhages, ischemia, diabetes, glaucoma, but also provide early diagnosis of neurological diseases that cause changes in the retina, such as Alzheimer's disease. Our project aims to investigate and refine the hyperspectral camera technology by photographing healthy retinas. Furthermore, we intend to also examine people with diseases that affect the retina such as glaucoma and age-related macular changes, diabetes, retinal detachment and compare diagnostic accuracy with other available techniques. With improved examination technology, it is possible to sharpen treatment and in some cases perhaps also advance adequate treatment.

Investigational device:
	
Mantis Photonics' hyperspectral camera for non-invasive retinal examination (i.e., hardware device): CB200-10nm-160x160-2

Inclusion criteria:
	
For inclusion in the investigation, the patient-subjects must fulfill all of the below criteria prior to enrollment:
 
 1. Age > 18 years. 2. Ophthalmological disease, disorder, illness or problem involving the retina 3. Provision of informed consent i.e., subject must be able to understand and sign the patient information and consent form. 
For inclusion in the investigation, the healthy subjects must fulfill all of the below criteria prior to enrollment:
 
 1. Age >18 years. 2. Without known eye disease. 3. Provision of informed consent i.e., subject must be able to understand and sign the patient information and consent form.

Exclusion criteria:
	
Patients-subjects who meet any of the below criteria will be excluded from the investigation:
 
 1. Patients with narrow angle glaucoma 2. Inclusion in other ongoing investigations at present that would preclude the subject from participating in this investigation as judged by the Principal Investigator. 
Healthy subjects who meet any of the below criteria will be excluded from the investigation:
 
 1. Presence of eye disease, eye trauma, diabetes or pregnancy.

	
3. Inclusion in other ongoing investigations at present that would preclude the subject from participating in this investigation as judged by the Principal Investigator.

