
Study objectives:
	
Primary objective: To evaluate the performance of the hyperspectral camera for non-invasive retinal examination in order to improve the diagnosis of diseases affecting the retina or central nervous system.
 
Secondary objective: To investigate the possibilities of the use of a hyperspectral camera for non-invasive retinal examination.
 
Safety objective(s): To evaluate the safety of the hyperspectral camera for non-invasive retinal examination by assessment of device deficiencies and adverse events, non-serious and serious, rated for causality.

Study endpoints:
	
Primary endpoints: To evaluate the effectiveness of the hyperspectral imaging of retinal changes by detecting structures and conditions in the retina and to compare the hyperspectral imaging with other diagnostic techniques. More specifically, can the hyperspectral camera detect the different structures of the retina based on spectral distribution? Can the hyperspectral camera detect differences in oxygenation levels between arteries and veins in healthy retina and retina with disease?
 
Secondary endpoint: To investigate if additional signs of reduced oxygenation can be seen in retinal disease. More specifically, can optic nerve thinning be detected by hyperspectral camera? Can hyperspectral imaging detect changes that are not measurable with other examination modalities and do these differ from normal retinal changes?
 
Safety endpoint(s):
 
 1. Incidence of AE/ADE/SAE/SADE/DD. 2. Incidence of AE/ADE/SAEE/SADE/DD leading to withdrawal of a subject. 
The experience of having a temporary, benign after-image of the flash lamp for a brief period is common. The mydriatic eye drops can be temporary unpleasant (pain and discomfort, redness, itching and/or blurriness). Those effects are expected and explained during the informed consent phase before including the subject in the trial. Those effects should not be qualified as unacceptable risks of harm to the subject, and therefore those effects are no reason to stop the clinical investigation, unless the subject wants to withdrawal from the clinical investigation.

Planned duration of the clinical investigation:
	
Estimated date of first subject enrolled: Q3 2022.

Estimated date of last subject completed: Q2 2023.

Estimated date of end of clinical investigation (database lock) is Q4 2023.

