REQ-HW-9	The flash lamp spectrum must be known and must be stable because the software requires this information to calculate the relative reflectance of the retina.

The Mantis Photonics hyperspectral camera is based on a patented solution where the incoming light is collected so that only parallel beams are passed through a collimator, then the light is diffracted and reaches a micro lens array and is then captured in the camera. Figure 1 shows the conceptual design of the Mantis Photonics hyperspectral camera - Imaging principle.

[figure not shown]

Figure 1

Figure 2 and figure 3 illustrate the electric circuit for powering the Mantis Photonics hyperspectral camera and synchronizing it with the flash lamp trigger box - Electrical circuit to power the camera and connect the camera to the triggerbox.

[figure not shown]

Figure 2

[figure not shown]

Figure 3

3. DESCRIPTION OF THE REQUIREMENTS OF THE MANTIS PHOTONICS SOFTWARE LINKED TO THE CAMERA:

ID	Description
REQ-SW-3	The software must allow to control the camera in software trigger mode (see REQ-HW-7).
REQ-SW-4	The software must allow to control the camera in hardware trigger mode, initiating the camera to wait for the TTL signal from the flash lamp (see REQ-HW-6).
REQ-SW-5	The software must show the most the frequency slices at 450 nm to 700 nm in steps of 50 nm to the operator for revision of the retinal scan quality (see REQ-MED-7). This conversion should be under 30 seconds to allow the operator to take corrective action if needed.

4. MEDICAL REQUIREMENTS OF THE MANTIS PHOTONICS SET-UP:

ID	Description
REQ-MED-1	The test set-up must be safe for medical use, both for the patient and for the operator.
REQ-MED-2	The flash lamp must be safe for medical use, both for the patient and for the operator.
REQ-MED-3	The flash lamp settings, including light intensity and flash duration, must be safe for medical use.
REQ-MED-4	The set-up operation must be comparable or identical to the use of other retinoscopy cameras used by trained ophthalmologists and optometrists.
REQ-MED-5	The patient experience must be comparable or identical to the use of other retinoscopy cameras used by trained ophthalmologists and optometrists.
REQ-MED-6	The set-up must allow a 15° angle view of the retina to allow taking retinal scans with sufficient view of the retina to identify ischemia and/or contain the required regions of interest for the Alzheimer’s disease classification algorithm.

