6.4. Description of the clinical procedures and methods relating to the clinical investigation

Recruitment of healthy subjects is done through local advertising. Recruitment of patient-subjects with eye disease is done at the clinic Sundets Öganläkare.

Coordinated registration and allocation of participant trial numbers will be required to enroll all participants (see section 6.3). The Principal Investigator ensures through the Informed Consent Form that the trial objective, process and all trial subject rights are clear to the subject.

All participants (healthy subjects and patient-subjects) are considered to be enrolled into the clinical trial following the informed consent is signed, the evaluation of the medical history and the inclusion criteria, confirmation of eligibility, completion of the registration, allocation of the participant trial number and the investigation performance phase.

The overall purpose is to investigate if the investigational device can produce clear hyperspectral imaging of retinal changes by detecting structures and conditions in the retina and to compare the hyperspectral imaging with the expert diagnosis, as well as to investigate if additional signs of reduced oxygenation can be seen in retinal disease.

The admission visit (visit 1) is carried out as planned with visual acuity, refraction, pressure, field of view (if applicable), OCT and corneal microscope examination. Records of age and sex, other diseases and treatment are obtained. The subject will be administered pupil dilating drops of tropicamide 1% and phenylephrine hydrochloride 10% are instilled in each eye at the time of the examination. Images of the retina of the subject will be taken with the use of the Mantis Photonics hyperspectral camera by the medical staff members at the investigational site. The subjects are usually sent home after the image is taken when there are no inconveniences for the subjects.

The overview of the clinical investigation provides a review of each visit describing clinical investigation-related procedure(s) the subject undergoes during each visit:

Procedure	Visit 1 - part 1	Visit 1 - part 2	Visit 1 - part 3
	Admission & screening phase	Application of the investigation device phase	End phase
Informed consent	x		
Inclusion/exclusion criteria	x		
Medical history review	x		
Eligibility	x		
Administration of eye drops and flashlight taking image		x	
Adverse Events review		x	x
Clinical investigation end			x

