After the phases above, the retinal images are taken and analyzed. Researchers such as (Meinke 2007) have demonstrated how one can estimate the blood oxygenation at a given location (image pixel) based on the frequency absorbance spectrum. The reference frequency absorbance spectrum of fully oxygenated blood (100% oxygenation) and fully oxygen-depleted blood (0% oxygenation) are known and tabulated by comparing the pixel's frequency spectrum to the frequency absorbance spectrum of two reference curves allows us to estimate the oxygenation of the blood at the respective location.

We will compare oxygenation between arteries and veins. The largest artery and vein at the superior and the inferior temporal vascular tree will be marked for each eye. We will analyze 10 to 20 consecutive points from the papillary edge along the vascular tree to measure the mean vessel oxygenation level and the evolution of the oxygenation level. The initial image analysis can be followed by machine learning to distinguish between a normal retina and a retina affected by a disease (the ophthalmologist's diagnosis can be taken as ground truth).

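### Eye-disease exclusions differ between healthy subjects and patients, and the oxygenation estimate has no term for the ocular media, so group differences can come from the lens or other media instead of the retina

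*Combined protocol and SAP*

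**What the plan says.** **Who may enter.** Section 6.3 excludes healthy subjects for "Presence of eye disease, eye trauma, diabetes or pregnancy". For patients it lists two exclusions: "Patients with narrow-angle glaucoma" and participation in a conflicting investigation. Patient inclusion in 6.3 reads "Ophthalmological disease, disorder, illness or problem"; the synopsis is narrower, with "Ophthalmological disease, disorder, illness or problem involving the retina". Neither version mentions cataract, lens status, or corneal or vitreous opacity.

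**How oxygenation is obtained.** REQ-HW-9 in 2.1 requires a known, stable lamp spectrum because "the software requires this information to calculate the relative reflectance of the retina". Section 6.4 then estimates oxygenation by comparing each pixel's spectrum with reference curves for fully oxygenated and fully deoxygenated blood.

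**Where the groups are compared.** The synopsis primary endpoint asks: "Can the hyperspectral camera detect differences in oxygenation levels between arteries and veins in healthy retina and retina with disease". Section 5.2 lists signs of reduced oxygenation in retinal disease as a secondary outcome. Section 6.4 allows a later step of "machine learning to distinguish between a normal retina and a retina affected by a disease", with the ophthalmologist's diagnosis as a possible reference.

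**What is already collected.** Visit 1 (6.4) includes "OCT and corneal microscope examination", and age is recorded. No grading of the media, and no analysis rule based on it, is described.

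**The concern.** Light reaching the sensor has crossed the cornea, lens and vitreous on the way in and again on the way out. If those media absorb or scatter differently in patients and in healthy subjects, the pixel spectrum changes although the retina does not. The eligibility rules allow exactly that imbalance: a known opacity keeps a healthy volunteer out but not a patient. Recruitment may add to it. Healthy subjects come from local advertising and patients from an eye clinic, with no age matching and no upper age limit.

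At stake is how any healthy-versus-patient difference in saturation is interpreted, and whether a classifier has learned retinal disease or lens haze. The imbalance follows the group label, so recruiting more patients would not remove it.

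**Working it through.** The plan has no sample-size calculation, SD or effect size, so there is no figure of its own to reproduce; 100 + 20 = 120 is only a sum. The check has three parts.

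**1. Reading the text.** The asymmetry is in the current 6.3. It survives under the synopsis wording, because a retinal patient may also have a cataract or an artificial lens. Under the 6.3 wording, cataract alone would qualify. Sections 2.1 and 6.4 describe no media term, and 7.4 describes no split or adjustment.

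**2. How far a media effect could move a reading (illustration).** Assumptions from outside the documents: approximate haemoglobin absorption shapes, and an extra absorption exp(-(wavelength - 450)/50) scaled to 0.25, 0.5 or 1.0 of the mean haemoglobin signal. The two-curve fit was run over 450-700, 500-600 and 500-700 nm. Ranges are over these three windows.

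| Scale | Artery, true 97% | Vein, true 60% | Artery-vein, true 37 |
|---|---|---|---|
| 0.25 | 94.5-97.4 | 58.6-62.2 | 35.2-36.5 |
| 0.5 | 92.2-97.7 | 57.2-64.2 | not tabulated |
| 1.0 | 87.9-98.4 | 54.8-67.7 | 30.7-35.0 |

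At scale 1.0 the worst shifts are 97 - 87.9 = 9.1 points (artery), 67.7 - 60 = 7.7 (vein) and 37 - 30.7 = 6.3 (difference). At 0.25 they are 2.5, 2.2 and 1.8. So the within-eye difference is less exposed, but not immune. The sign of the absolute shift changes with the wavelength window.

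**3. What that could do to a group comparison (illustration).** Assume haze in a share p of patients and in no healthy subject, a bias b in a hazy eye, one value per subject, and no true retinal difference.

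- Apparent group difference = p x b. With p = 10-50% and b = 2-10 points: 0.10 x 2 = 0.2 up to 0.50 x 10 = 5.0 points.
- SE = SD x sqrt(1/20 + 1/100). At SD 5 (assumed), SE = 1.225 and the 95% half-width is 1.96 x 1.225 = 2.4 points. At SD 10 it is 4.8.
- Approximate chance that the 95% interval excludes zero on the side of the bias, at SD 5 = Phi(p x b / 1.225 - 1.96): 23% for 30% x 5 points, 69% for 30% x 10, 98% for 50% x 10. For a bias of 0.2 to 0.5 points it is 4-6%, close to nothing of note.
- A marker that sees only haze has sensitivity p and specificity 1, so AUC = 0.5 + p/2: 0.55, 0.65 and 0.75 at 10%, 30% and 50%.

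With equal haze in both groups, the first quantity is 0 and the AUC is 0.50.

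**The case against.** This is a pilot (3.4) aimed at feasibility and applicability (6.1), with descriptive statistics and no hypothesis test (7.1). Section 6.1 says no control group is defined, and machine learning is only optional. The outcome table in 5.2 lists structures, repeatability and healthy-retina levels as primary, none of which compares the groups. The synopsis contrast concerns arteries against veins, which are read through the same media. There are partial safeguards: the operator reviews wavelength slices for scan quality (REQ-SW-5), 3.3 allows grouping by data quality, and 7.3 summarises all baseline variables.

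Much of this stands. It narrows the point to absolute saturation, the classifier and, less strongly, the artery-vein difference. The harm is to interpretation, not to an error rate. It does not dispose of the point. The synopsis endpoint and the secondary outcomes still look at healthy against diseased retina, and descriptive differences will be interpreted. None of the safeguards is a media rule in the text supplied. REQ-SW-5 refers to REQ-MED-7, which is not in that text and cannot be judged.

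A reader might also infer that the analysis should be confined to clear-media eyes. The documents do not support going that far. Section 4.1 names haemorrhages and past retinal detachment surgery among the conditions of interest, and such a rule could drop those patients. Nor do they show that a corneal microscope examination grades the vitreous.

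**Conclusion.** The plan leaves the healthy-versus-patient oxygenation comparison, and any classifier, open to confounding by the ocular media. This follows from the eligibility text and the described measurement alone. It is worth correcting because the correction is cheap.

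A reader might infer that the readings do differ between the groups because of the media, or that patients will read falsely low. Neither is shown. The documents never mention cataract or haze and give no prevalence, and the illustrative absolute shift changes sign with the wavelength window. The 0.2 to 5.0 points and the AUC of 0.55 to 0.75 rest wholly on the assumed haze shares and, for the points, the assumed bias. They show that the effect could be trivial or could exceed the 2.4-point half-width at SD 5. Nor does the point undermine the healthy-retina targets (above 95% in arteries, below 70% in veins) or repeatability, since neither uses the group contrast.

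**What to change.** **Section 6.4.** Record per eye, from the visit 1 examination and before the images are read, lens status (natural clear, natural with opacity, artificial) and any visible media opacity.

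**Section 7.4.** Keep the all-eyes summary. Add a pre-specified table of every healthy-versus-patient oxygenation comparison, and of any classifier result, by media status, with clear-media eyes shown separately. Take age into account by bands or adjustment, because a lens coded as clear can still absorb more with age. State that a group difference not seen in clear-media eyes of similar age will not be attributed to the retina. In a small subgroup, its absence leaves the cause open and does not prove a media effect.

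**Section 6.3 and synopsis.** Reconcile the two versions of the patient inclusion criterion. The exclusions need not change.

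**Cost.** A few CRF fields, one more table and less precise subgroups. If half the patients had clear media and all 20 healthy subjects did, the half-width at SD 5 would be 1.96 x 5 x sqrt(1/20 + 1/50) = 2.6 points, against 2.4. Two equal age bands within that (10 against 25) would give 1.96 x 5 x sqrt(1/10 + 1/25) = 3.7 points each. The roughly 20 healthy subjects are the limit.

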2.2. Intended purpose

The Mantis Photonics hyperspectral camera for non-invasive retinal examination is built to capture retinal ischemia and amyloid-β accumulation in the retina using a hyperspectral retinal scan, based on its wavelength-dependent effect on light scattering. The intended purpose of the investigational device in the light of this clinical investigation is to evaluate the performance of the hyperspectral camera for non-invasive retinal examination in order to improve the diagnosis of diseases affecting the retina or central nervous system.

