3.1. Background

1. BENEFITS OF DETECTION OF LOW OXYGENATION REGIONS IN THE RETINA

The Western population is getting older. This is of course a positive development, but more and more people are also suffering from age-related diseases such as glaucoma and yellow spot changes that reduce vision and quality of life (Flaxman, et al. 2017). Diabetes is another disease whose complications affecting the retina are increasing in prevalence (Zimmet, et al. 2016).

The diagnosis of retinal diseases has improved in recent years with the advent of refined imaging techniques such as OCT and Ultrasound and functional tests such as automated perimetry. However, there is still a need to improve our understanding of the pathogenesis of several eye-related diseases. In the development of diabetic retinopathy, a disturbed oxygenation of the tissues with elements of hypoxia plays a role (Hardarson en Stefánsson 2012). In the development of glaucoma, there is also a discussion of an element of ischemia as an etiology (Lee, et al. 2021). To measure the degree of perfusion in the retina, angiography can be performed. However, this is time-consuming and invasive, also associated with certain risks for patients. Therefore, there is a need to improve and simplify the diagnosis and to measure the oxygenation of retinal tissues in a more convenient way.

Through shared ontogeny, the retina shares similar functions to the brain and spinal cord in terms of anatomy, functionality and immunology (De Groef en Cordeiro 2018) (London, Benhar en Schwartz 2013). There are several ocular markers for stroke and MS (London, Benhar en Schwartz 2013). There are also several similarities between disease markers for Alzheimer's disease, age-related macular disease and glaucoma (Sivak 2013). In Alzheimer's disease, which primarily affects the brain, increased beta amyloid deposition is also seen in the retina and in patients with glaucoma and age-related macular disease, increased deposition of beta amyloid and tau protein, for example, is seen in the tissues (Sivak 2013). Good retinal imaging and functional testing is therefore important to detect diseases affecting the retina but also as a means of detecting diseases that do not primarily affect visual function. The retina is therefore opening up as a structure suitable for non-invasive detection not only of retinal diseases but also an opportunity for early diagnosis and monitoring of, for example, Alzheimer's disease.

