5.2. Objectives

The primary objective and outcome variable are shown in the table below:

Primary objective	Primary outcome variable
To evaluate the performance of the hyperspectral camera for non-invasive retinal examination in order to improve the diagnosis of diseases affecting the retina or central nervous system.	Effectiveness of the hyperspectral imaging of retinal changes and retinal structures in terms of detecting: 
 - Different structures of the retina based on spectral distribution. - Ability to measure the blood oxygenation with an acceptable repeatability - Demonstrate differences in blood oxygenation levels for healthy retinas; above 95% in arteries and below 70% in veins.

The secondary objective and outcome variable are shown in the table below:

Secondary objective	Secondary outcome variable
To investigate if additional signs of reduced oxygenation can be seen in retinal disease. More specifically, can optic nerve thinning be detected by hyperspectral camera? Can hyperspectral imaging detect changes that are not measurable with other examination modalities and do these differ from normal retinal changes?	Effectiveness of the hyperspectral imaging in terms of detecting: 
 - Signs of reduced oxygenation be seen in retinal disease Ischemia detection in the retina. - Optic nerve thinning. - Changes that are not measurable with other examination modalities.

The safety objective and outcome variables are shown in the table below:

Safety objective	Safety outcome variable
To evaluate the safety of the hyperspectral camera for non-invasive retinal examination by assessment of device deficiencies and adverse events, non-serious and serious, rated for causality.	
- Incidence of AE/ADE/SAE/SADE/DD.- Incidence of AE/ADE/SAEE/SADE/DD leading to withdrawal of a subject.

6. Design of the clinical investigation

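### The healthy-subject criteria do not exclude known central nervous system disease, although the plan says such disease leaves signs in the retina and makes it part of the device's target

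*Combined protocol and SAP*

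**What the plan says.** The healthy criteria are the same in the synopsis and in section 6.3. On health status, inclusion asks only for "Without known eye disease". The exclusions are "Presence of eye disease, eye trauma, diabetes or pregnancy", and "Inclusion in other ongoing investigations at present that would preclude the subject from participating in this investigation as judged by the Principal Investigator". The second is not a health criterion. The consent criterion adds that the "subject must be able to understand and sign the patient information and consent form".

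Elsewhere the plan describes retinal signs of brain disease. Section 3.1 states: "There are several ocular markers for stroke and MS". Of Alzheimer's disease it says that "increased beta amyloid deposition is also seen in the retina", and it cites a report that machine learning on hyperspectral images separated people with Alzheimer's disease from healthy people. Section 2.2 says the camera is "built to capture retinal ischemia and amyloid-β accumulation in the retina". The primary objective (synopsis and section 5.2) concerns diagnosis of disease of the retina or of the central nervous system.

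The healthy group serves three purposes:
- One primary outcome in section 5.2 is "Demonstrate differences in blood oxygenation levels for healthy retinas; above 95% in arteries and below 70% in veins".
- The secondary objective in section 5.2 asks whether the changes seen differ from those of a normal retina.
- Section 6.4 allows a later machine-learning step that separates normal from diseased retinas, with the ophthalmologist's diagnosis as a possible ground truth.

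**The concern.** A reference group should be free of the conditions that the device is meant to pick up. Here the plan names certain brain diseases as visible in the eye or retina, counts central nervous system disease in its primary objective, and then sets healthy criteria that look only at the eye, diabetes and pregnancy. Excluding diabetes shows that the plan accepts the principle of removing a systemic disease that alters the retina. It does not carry that principle through to the neurological diseases it discusses.

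Two uses of the healthy group are at stake. The range taken as normal could include true disease signs, which weakens the contrast with patients. In a classifier trained on the ophthalmologist's diagnosis, a volunteer with retinal amyloid but no eye diagnosis would carry the label normal, so a correct detection would count as a false positive.

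**Working it through.** The plan gives no sample-size or power figure to reproduce: section 7 describes a descriptive study without hypothesis testing. The main check is a comparison of sections.

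**Step 1: who qualifies.** Take a volunteer over 18 with multiple sclerosis, a past stroke, or early Alzheimer's disease with capacity to consent, and with no known eye disease, trauma, diabetes or pregnancy. Every inclusion criterion is met and no exclusion applies. The consent criterion stops only people too impaired to consent.

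**Step 2: whether another provision closes the gap.**
- Sections 2.5 and 6.4 have the medical history reviewed and other diseases recorded, but no rule makes a neurological diagnosis exclusionary.
- Section 6.1 describes the volunteers as people in whom no retinal pathology is known or suspected. This is a description rather than a numbered criterion, and it concerns the retina only.
- Section 6.3 lets the investigator withdraw a subject at discretion, possibly after the images have been seen. Its rule on incorrectly enrolled subjects does not apply, because these people meet the criteria.

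**Step 3: weight of one subject.** About 20 healthy subjects are planned (sections 6.3 and 7.2), so one is 1/20 = 5%, two are 10% and three are 15%.

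**Step 4: chance of at least one affected volunteer.** The documents give no prevalence p among volunteers, so p is an assumption. The chance is 1 − (1 − p)^20:

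| Assumed p | At least one of 20 |
|---|---|
| 1% | 18% |
| 2% | 33% |
| 5% | 64% |
| 10% | 88% |

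**Step 5: low systemic oxygen (secondary, by inference).** The plan sets an absolute arterial limit of 95% but never mentions systemic oxygen, and section 6.4 lists no measurement of it. Suppose k of 20 volunteers have a true arterial value d points lower than the rest. The group mean then falls by k × d/20. All values of k, d and the mean of the others are assumptions.

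| k | d | Fall | Mean if others 97% | Mean if others 96% |
|---|---|---|---|---|
| 0 | – | 0 | 97 | 96 |
| 1 | 5 | 0.25 | 96.75 | 95.75 |
| 1 | 10 | 0.5 | 96.5 | 95.5 |
| 2 | 5 | 0.5 | 96.5 | 95.5 |
| 2 | 10 | 1.0 | 96.0 | 95.0 |
| 3 | 5 | 0.75 | 96.25 | 95.25 |
| 3 | 10 | 1.5 | 95.5 | 94.5 |

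The mean stays above 95% unless two or three volunteers are 10 points lower and the others average only 96%.

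**The case against.** The strongest reply is that this is a feasibility pilot whose stated purpose (section 5.1) is the observation of retinal oxygenation. No outcome in section 5.2 measures amyloid. Section 3.1 says that markers or deposits exist, not that Alzheimer's disease, stroke or multiple sclerosis changes the saturation of retinal vessels. The classifier is optional. History and other diseases are recorded and all data are listed, so an affected volunteer could be identified, withdrawn and replaced.

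Much of this stands. A reader might infer that brain disease would spoil the 95%/70% outcome; nothing in the documents links the two. A reader might also call the criteria a contradiction. They are an incomplete list that is inconsistent with the plan's background, since no passage promises a group free of neurological disease.

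On low oxygen, a reader might infer that a correct reading in an affected volunteer is scored as a device failure, so that one to three such people cap the success rate at 95% to 85%. That needs a pass/fail rule per subject. The plan has none: it does not say whether the limits apply per vessel, per subject or to a mean. On a group mean, 18 volunteers at 97% and two at 90% give (18 × 97 + 2 × 90)/20 = 96.3%, still above the limit.

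What does not stand is that the gap is already handled. Recording a disease and permitting withdrawal is weaker than a rule fixed before the scan.

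**Conclusion.** The point holds as a cheap improvement to the reference group. Known central nervous system disease can enter a healthy group of about 20, at 5% per subject, and this bears on the normal-retina comparison and on any classification. That conclusion rests on the plan's own statements and needs no assumed figure. How likely such volunteers are cannot be judged from the documents; the probabilities above only show scale.

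The low-oxygen part is weaker. It is inferred from the absolute arterial limit, and every saturation value used is assumed. It justifies a separate summary or an exclusion, but no claim that the primary outcome would fail.

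**What to change.** In section 6.3 and the synopsis, add known central nervous system disease (such as dementia or cognitive impairment, multiple sclerosis or stroke) to healthy exclusion 1. Apply it at the medical history review in visit 1 part 1, before scanning. List any such subject already scanned separately from the healthy summary.

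As a secondary change, exclude or summarise separately any healthy volunteer whose recorded history shows a condition known to lower arterial oxygen, and say in advance which of the two will be done.

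Both changes use history already collected, so no new test is needed. A few volunteers will be turned away. Undiagnosed disease will still be missed, and history alone is an imperfect guide to arterial oxygen.
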